Harnessing the Power of Technology: MOMBA for Postpartum Smoking NCT02237898

09/07/2017

Overview: Through a pilot, randomized control trial tested the effectiveness of Momba Live Long (the Momba Live Long application and sensor) on 7-day point prevalence of smoking abstinence rates i) at the end of the trial and ii) at 3-month follow-up as determined by the Timeline Follow Back instrument and number of negative breath tests.

The randomized controlled trial of Momba Live Long utilized a control group which received financial incentives at an in-person office/clinic visit based on expired CO levels obtained through the piCO+TM CO sensor compared to the MoMba Livelong application. We used results from frequently administered assessment instruments over the course of an 3-month period and subsequent 6- and 12-month follow ups to assess outcomes and to examine the reliability and validity of assessment measures, and key methodological parameters, such as effect size, proportion of eligible and willing study participants, attrition rate, time necessary for data collection, and necessary skill sets for CMHAs. The RCT involved an intervention arm (10 women who receive Momba Live Long) and "control" arm (10 women who receive financial incentives delivered in-person in the office). Participants were randomized using a number generation mechanism provided to the CMHAs who are screening and enrolling women.

Intervention Group (Momba Live Long): The intervention group received a smartphone, data plan, Momba Live Long, including the Bluetooth enabled CO sensor, and training from a CMHA on its use. The intervention group did most of its CO tests remotely, outside of a baseline, 3-month end point assessment, and 6-month and 12-month follow-ups. However, participants also came n for the first 5 days of week 1 to be trained on how to use the Sensordrone and Momba Live Long app. As part of this training, we showed the intervention group participants a Demonstration Video and a Powerpoint Presentation about how to use the Momba Live Long Application. Intervention group participants came to the office for a visit in Week 4 and Week 8 to calibrate the Sensordrone and to submit a urine specimen.

Control Group: Control group mothers received traditional, in-office contingency management to prevent smoking relapse. Financial incentives were delivered according to the same schedule at the same frequency as those delivered to mothers on Momba Live Long. The exception was that mothers in Momba Live Long will also receive payment for completing tasks that promote abstinence. Overall, the amount of Contingency Management incentives in the two groups were similar. Thus, we were not directly comparing the effectiveness of contingency management that has already been well established, but rather we assess the effectiveness of contingency management delivered over a smartphone application vs. traditional contingency management in an office setting. Women in each condition were provided with the Staying Smoke Free curriculum. Mothers in the control condition completed the same assessment battery and according to the same schedule as participants in the Momba Live Long application group and were compensated similarly. During the first 3 months, control group participants completed assessments with staff during office visits. In months 4-12, surveys were administered via Qualtrics links on personal smartphones, over the phone with research staff, or by mailing the surveys to and from participants' homes. Control group CM breath tests were conducted with the piCO+TM, considered as "traditional" Contingency Management. They also completed Sensordrone CO tests for comparison purposes with the Intervention Group. Control participants were also be compensated for attending each scheduled CO test office visit.

Participants: Women who were smoking in the second or third trimester of pregnancy, with no complicating general medical or psychiatric conditions (including other substance use disorder) were eligible. Women were not receiving other smoking cessation medication. Mothers were not eligible to participate if they were planning to move out of the New Haven area in the next 15 months after study enrollment, had medical complications that would interfere with testing the Sensordrone, or were actively suicidal, psychotic or unable to provide informed consent.

Screening and Enrollment: We used rolling enrollment (over a

2-month period) and women were followed up to 15 months after study start date. Following a brief description of the study by the Community Mental Health Ambassadors (CMHAs), mothers who live in New Haven and have been trained as research assistants, at a woman's prenatal visit at YNHH or at a community hub visit, women were screened in person or over the phone for smoking status using the Fagerstrom Test for Nicotine Dependence (FTND), a sixitem self-report form that gives a quantitative measure of the severity of nicotine dependence.(37) The study screening form collected personal contact information and significant other contact information as well as demographics and health history. An abbreviated version of the Mental Test Score (33) was used to determine any cognitive impairment or inability to provide informed consent. The CMHAs performed a brief in-person or phone screening, a more complete in-office screening for those still eligible (including submitting a urine specimen to confirm pregnancy and cotinine and to exclude other drug use), and obtained written informed consent.

The screening consent also included a Release of Information (ROI) from YNHH and other local medical providers to obtain medical records about pregnancy and smoking status, pregnancy complications and medical exclusion criteria. These records were reviewed to confirm medical conditions which may interfere with the results of the Sensordrone. A second Release of Information was completed with the consent to participate requesting information about pregnancy and delivery status.

All women were approached until the target enrollment has been reached.

Delivery of the Momba Live Long Intervention: After completion of screening, consents and intake interview, women were provided with a smartphone and data plan, a carbon monoxide sensor compatible with their phone, access to the Momba Live Long application, and training on its use by the CMHAs. This exchange of equipment and training occurred at our office at the end of week 1 of study start date. Testing of CM lasted 12 weeks.

In office monitoring: Women were required to come into the office to perform in-person CO breath tests using the Sensorcon SensordroneTM and Bedfont piCO+TM in order for us to continue to compare data on the reliability and validity of the Sensordrone. At each office visit women completed additional questionnaires and urine tests to measure cotinine levels to provide additional data on the validity of the SensordroneTM and other drug use (to see if these other drugs affect how well the Sensordrone performs).

Financial incentives were delivered based on the CO breath test. We followed standard protocols for in office monitoring of smoking abstinence and the delivery of financial incentives in

[figure not shown]
pregnant and postpartum women. These included the provision to all participants of the Smoke Free curriculum in addition to the financial incentives to promote abstinence. We required women to report to our clinical office for 5 consecutive days for abstinence monitoring the first week of study enrollment. The frequency of in-office abstinence monitoring decreased to twice weekly in week 2. Frequency of visits in weeks 3-12 depended on accuracy of the Sensordrone; at most, in weeks 3-8 it was twice per week and in weeks 9-12 it was once per week. In-office visits for breath tests were not required after week 12.

Administration of Standardized Measures: All follow-up measures, with the exception of baseline, post, and 6-month post CM and 12-month post CM follow-ups (administered in-office by research assistants, and mostly on a laptop computer) were administered via the Momba Live Long application. Mothers were prompted by the Momba Live Long application upon login and push notifications, to complete the questionnaires at specified intervals. The outcome measures we assessed were: (1) acceptability of the smartphone application to low-income, pregnant women (as defined by the percentage of women who would recommend the site to a friend); (2) point and 7-day smoking prevalence as determined by the Timeline Follow Back assessment, and # of negative breath tests, (secondary outcome); and (3) correlation coefficients between the piCO+TM and the Sensordrone TM specific to expired CO measurement and verified through urine cotinine levels.

The Phen-X was used to generate diagnoses of depression, anxiety disorders (including trauma and stress disorders), and substance use disorders at baseline and 6-month follow-up. We will collect detailed information about enrolled mothers from the eligibility screening interview and baseline and outcome assessments. Specific instruments utilized and delivered via the Momba Live Long application and the in-person office visits included:

Smoking cessation outcome assessments- In addition to the results of the CO monitor (which only can detect nicotine levels up to 2 to 3 hours after a cigarette), urine will be tested in the office with a qualitative cotinine cassette test from Redwood Toxicology Laboratory and sent to the Dept. Laboratory Medicine, at Yale School of Medicine for confirmation and cotinine levels. Other drugs tested in the office using cassette and dip tests from Redwood Toxicology Laboratory will be for amphetamines, barbiturates, benzodiazepines, cocaine, methadone, Methamphetamine, opiates, PCP, THC and Oxycodone.Self-report of cigarette smoking history was collected with the timeline follow-back (TLFB) for the past 28 days. Measures at post, 6M post CM and 12M post CM included the Fagerstrom Test for Nicotine Dependence, and the self-report of cigarette smoking history using the timeline follow-back (TLFB) for the past 28 days.

Proposed Analytic Plan: The goal of the proposed analysis is to determine the feasibility of the web-based intervention and acceptability and perceived value of the Momba Live Long smartphone-based system. We will evaluate progress toward these goals looking specifically at: (1) ensuring a process exists to assess best practices and participant opinion and integrate them into Momba Live Long and (2) ensuring procedures exist to support and monitor intervention delivery and dissemination.

To quantitatively evaluate the *feasibility* and *acceptability* of Momba Live Long to postpartum women we will begin by calculating the number of women screened and eligible and enrolled. We will collect data on reasons women are not enrolled. We will consider a participation rate of $\geq 60\%$ for eligible women between screening and enrollment as supportive of feasibility. We will evaluate retention and set a threshold of 80% for the Momba Live Long group. Since feasibility also depends upon compliance to the challenges or office visits through which contingency management is delivered, we will use challenge completion and in-office visit attendance to assess compliance. Mixed-effects regression models will be conducted as outlined above for group comparisons. Because number of visits attended is a count variable, random effects regression with a negative binomial model will be used which is appropriate for count data.(45) Additional procedures to evaluate abstinence from smoking are described below.

Data Analysis for Pilot RCT: Descriptive statistics will summarize the data on all screened and randomized subjects. Baseline demographic and clinical characteristics for the randomized groups will be compared using chi-square tests for categorical variables and analysis of variance for continuous variables. All continuous variables will be examined for adherence to the normal distribution using normal probability plots and Kolmogorov-Smirnov tests. Dropouts and completers will also be compared on baseline characteristics using the same approach. Data analyses will be conducted using the intent-to-treat principle. We will use mixed-effects regression models to compare the two groups (Momba Live Long vs. in-office contingency management) using SAS PROC MIXED version 9.3. These models allow for different numbers of observations per subject, use all available data on each subject, and are unaffected by randomly missing data. They are flexible in modeling the correlation structure of the data. In each model, we will include fixed effects of time, group (Momba vs. in-office) and time by group, and random subject effects. If there are concerns of informative dropout and/or informative intermittent missing data, we will use pattern mixture models to perform sensitivity analyses to our main analyses.

For the RCT dependent variables are the 7-day point prevalence of smoking abstinence rates i) at the end of the trial and ii) at 3-month follow-up. We will also compare 2-week continuous smoking abstinence rates at these time points. Smokers are considered abstinent based on self-reported smoking abstinence verified by CO levels <6 ppm and self-report abstinence based on the Timeline Follow Back. (50) Because abstinence is categorical, a binary random effects logit model will be used. (51) As a secondary analysis, we will add an indicator variable for intensity of utilization for Momba Live Long application to the model in order to determine if it contributes significantly to response. Given that this is a pilot, we are not powered

to detect a significant difference on our outcomes. However, we will develop effect sizes to estimate power for a larger study and we will evaluate the direction and consistency of effects. We use guidelines for Stage 1b studies, which suggest 15-30 participants per cell. (52) For the outcome of 7-day point prevalence for smoking abstinence at the end of the trial, and 15 subjects per condition, a 2-tailed alpha of .05 we will have power of 90% if we have the same effect size found in other studies of contingency management with perinatal women smokers. (34) In all likelihood, the effect will be smaller for the 3-month outcomes. However, these results will provide a reasonable estimate with which to power a larger study.

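### Only a minority of the pairs behind the Sensordrone validity correlation come from sensors in home use, so it can miss drift or offset in the remote readings

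*Combined protocol and SAP*

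**What the plan says.** The third outcome, under Administration of Standardized Measures, is "correlation coefficients between the piCO+TM and the Sensordrone TM specific to expired CO measurement and verified through urine cotinine levels". Neither the Proposed Analytic Plan nor Data Analysis for Pilot RCT says how these coefficients are computed, or whether by arm, by unit or by time since calibration.

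The pairs are office pairs. In office monitoring states: "Women were required to come into the office to perform in-person CO breath tests using the Sensorcon SensordroneTM and Bedfont piCO+TM", and gives the purpose: "in order for us to continue to compare data on the reliability and validity of the Sensordrone". Its schedule names no arm. It has five days in week 1, two visits in week 2, at most two a week in weeks 3-8 and at most one a week in weeks 9-12. Frequency in weeks 3-12 depends on how accurate the Sensordrone proves. No office breath tests are required after week 12.

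The arm-specific text is narrower. Under Intervention Group: "The intervention group did most of its CO tests remotely, outside of a baseline, 3-month end point assessment, and 6-month and 12-month follow-ups". That section adds five training days in week 1, and then "Intervention group participants came to the office for a visit in Week 4 and Week 8 to calibrate the Sensordrone". On the handover of the sensor, Delivery of the Momba Live Long Intervention says: "This exchange of equipment and training occurred at our office at the end of week 1 of study start date". Control women earn incentives on the piCO+, and the Control Group section adds: "They also completed Sensordrone CO tests for comparison purposes with the Intervention Group".

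**The concern.** The app arm depends on a sensor that a woman carries and uses at home for weeks. Its readings determine her incentives and can enter the count of negative breath tests, and the plan judges CO against a fixed 6 ppm cut-off. What needs validating is therefore that sensor, in that use, some weeks after calibration.

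The stated outcome does not isolate this. Week-1 pairs precede home use, and control pairs come from women tested in the office. Two of the visits named for Momba women after handover are calibration visits. If the paired test follows calibration there, it describes a corrected sensor and not the one that produced the preceding remote readings.

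A correlation is also a weak measure for this purpose. It does not change at all if every Sensordrone reading is off by the same constant, and it changes little if the error sits in a minority of pairs. A drifting home unit could then sit behind a coefficient that looks excellent.

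**Working it through.** The plan gives no number of pairs or precision target for this outcome, so there is no figure to reproduce. The check is a count from the visit schedules.

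**Inputs.** There are 10 women per arm (Overview). Each woman has 5 office days in week 1, before handover. The general maximum is 5 + 2 + (6 × 2) + (4 × 1) = 23 office tests per woman, of which 18 come after week 1. The office visits named for Momba women between handover and 3 months are week 4, week 8 and 3 months, or 3 in all. Two week-2 visits are added if the general schedule applies to them.

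**Formula.** Let h be the paired visits per Momba woman after handover, and c the paired visits per control woman after week 1.

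Home-use share = 10h / [10(5 + h) + 10(5 + c)] = h / (10 + h + c)

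| Reading of the schedule | h | c | Home-use pairs | Share | At calibration visits |
|---|---|---|---|---|---|
| Momba arm-specific visits; controls at maximum | 3 | 18 | 30 of 310 | 9.7% | 20 of 30 |
| Same, plus week 2 for Momba | 5 | 18 | 50 of 330 | 15% | 20 of 50 |
| 23 tests per Momba woman, most remote (at most 11 in office); controls at maximum | 6 | 18 | 60 of 340 | 18% | 20 of 60 |
| Momba arm-specific visits; controls at an assumed 10 visits (5 + 2 + 3) | 3 | 5 | 30 of 180 | 17% | 20 of 30 |
| Same, plus week 2 for Momba | 5 | 5 | 50 of 200 | 25% | 20 of 50 |
| General maximum in both arms | 18 | 18 | 180 of 460 | 39% | 20 of 180 |

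If Momba women attend no more office visits than controls (h ≤ c ≤ 18), the share is largest at h = c = 18, which gives 18/46 = 39%. The power statement uses 15 women per condition instead of 10. That scales the counts by 1.5 and leaves the shares unchanged.

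The table assumes full attendance, a paired test at every office visit, and use of the woman's own unit. The last is not stated. If another unit is used in the office, there are fewer home-use pairs.

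**How far the correlation moves.** This is a simulation on assumed inputs: 2,000 runs, independent readings, half of them from smokers, error SD 1 ppm on each device, and a loss of sensitivity in home-use sensors. Ignoring random error, a sensor that shows a fraction g of true CO reads below 6 ppm for any true value below 6/g.

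| Assumed loss | True CO read as <6 ppm | r, 30 of 310, pairs after calibration | r, 30 of 310, pairs before | r, 180 of 460, after / before |
|---|---|---|---|---|
| none | below 6 | 0.987 | 0.987 | 0.987 |
| 20% | below 6/0.8 = 7.5 | 0.986 | 0.983 | 0.976 / 0.975 |
| 40% | below 6/0.6 = 10 | 0.982 | 0.971 | 0.937 / 0.932 |
| 50% | below 6/0.5 = 12 | 0.979 | 0.962 | 0.907 / 0.899 |

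Even a loss that lets true readings of almost 10 ppm pass leaves the overall coefficient at 0.93 or higher. The documents give no drift figure, so these losses only illustrate a range. A sensor that over-reads would err in the other direction.

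**The case against.** The strongest reply concerns the schedule. In office monitoring speaks of women in general and does not confine its visits to controls. Its accuracy-dependent frequency arguably suits the Momba arm better, since control incentives rest on the piCO+ anyway. On that reading home-use pairs reach 39%, and only 20 of 180 (11%) fall at calibration visits. This stands as a possible reading. It is a ceiling, however, and fits poorly with mostly remote testing on an incentive schedule shared by both arms. Even at 39%, no separate result for home-use sensors is stated.

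Three further points stand in part:
- **Accuracy-dependent visits.** These are an ongoing check, but no criterion is given.
- **The 3-month pair.** It is taken in the office, is not described as a calibration visit, and comes about four weeks after the week 8 calibration. It therefore tests the last interval, with one pair per woman.
- **Urine cotinine.** It is a further check on smoking status, but it does not measure a CO sensor's drift in ppm.

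A reader might infer more than the documents support:
- **That drift biases 7-day abstinence at the end of the trial.** This is not shown. The 3-month assessment is in the office, and abstinence also requires self-report on the Timeline Follow Back.
- **That the plan pools all pairs, or always pairs after calibration.** It is silent on both. Pairs taken before calibration at weeks 4 and 8 would be good drift checks.
- **That the sensors drifted.** Nothing in the documents shows this.

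**Conclusion.** The point holds in a limited form. The stated correlation draws on a minority of pairs from sensors in home use: about 10-15% on the arm-specific visits with controls at the maximum, 17-25% with controls at an assumed 10 visits, and 39% if the general maximum covers both arms. Twenty of these pairs fall at visits where the order of test and calibration is not set. The result can therefore miss drift or offset in the remote readings behind app-arm incentives and the count of negative breath tests.

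The spread in these shares arises mainly because the Intervention Group and In office monitoring sections do not give one schedule. The conclusion assumes that Momba women attend no more office visits than controls and bring their own sensor. It does not assume that drift occurred. In a 20-woman pilot this limits what can be claimed for remote monitoring and is inexpensive to repair.

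**What to change.** - At weeks 4 and 8, take the paired reading on the woman's own sensor before calibration. Do the same at the 3-month visit.
- For home-use units, report Sensordrone minus piCO+ differences by weeks since last calibration: mean bias, limits of agreement and classification at 6 ppm, allowing for repeated readings per woman. Show week-1 and control pairs separately. The correlation can stay as a supplement.
- Reconcile the two visit schedules, and state the accuracy criterion that governed visit frequency.
- If the data are already collected, report the order actually used and give the separate table.
- Show any assumed drift as a range.

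The cost is the order of two steps at existing visits and one extra table. The home-use estimate rests on fewer readings, so its confidence interval is wider.

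### Correlation is the only agreement statistic named for the Sensordrone against the piCO+, and an ordinary correlation cannot show an offset or scale error shared by all readings

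*Combined protocol and SAP*

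**What the plan says.** The device comparison is the third of three outcomes under Administration of Standardized Measures: "correlation coefficients between the piCO+TM and the Sensordrone TM specific to expired CO measurement and verified through urine cotinine levels". Its data come from office visits at which women had to "perform in-person CO breath tests using the Sensorcon SensordroneTM and Bedfont piCO+TM" (In office monitoring). That section gives the purpose as continued study of the Sensordrone's reliability and validity. Neither the Proposed Analytic Plan nor Data Analysis for Pilot RCT returns to the comparison.

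Three other checks on the sensor appear:

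- **Cotinine.** In office monitoring provides for "urine tests to measure cotinine levels to provide additional data on the validity of the SensordroneTM". Smoking cessation outcome assessments gives the assay: a qualitative cassette in the office, then laboratory confirmation and levels. No analysis links the result to the two CO devices.
- **Calibration.** Intervention women attended in weeks 4 and 8 "to calibrate the Sensordrone and to submit a urine specimen" (Intervention Group). No tolerance is stated.
- **Accuracy and visits.** "Frequency of visits in weeks 3-12 depended on accuracy of the Sensordrone" (In office monitoring). No statistic is attached.

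On use of the readings, abstinence is "self-reported smoking abstinence verified by CO levels <6 ppm" together with the Timeline Follow Back (Data Analysis for Pilot RCT). Incentives follow the CO breath test, and the number of negative breath tests is an outcome. "Control group CM breath tests were conducted with the piCO+TM" (Control Group), whereas "The intervention group did most of its CO tests remotely, outside of a baseline, 3-month end point assessment" (Intervention Group).

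**The concern.** Correlation measures how closely two sets of readings follow a straight line (Pearson) or share an order (Spearman). It does not ask whether the two devices give the same ppm value. If every Sensordrone reading were 10% low, or 1 ppm low, the correlation with the piCO+ would be exactly what it would have been without the error. A CO reading compared with a fixed ppm value would nevertheless be classified differently near that value. A high correlation could therefore be taken as evidence of validity for a sensor whose readings cannot be exchanged with the reference.

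At stake is first the third outcome itself, which on this statistic cannot support a claim that the two devices agree in ppm. Beyond that, the remote readings in the intervention arm depend on the supplied sensor, while control contingency-management tests used the piCO+, so a shared sensor error would fall mainly on one arm's remote readings.

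**Working it through.** The plan gives no figure for device agreement, so there is none to reproduce.

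**1. Algebra (no assumption about this trial).** Let x be the piCO+ reading and y the Sensordrone reading before the error. The reported reading is b + s·y, with s > 0. Pearson and Spearman correlations with x do not depend on b or s. A cut-off c on the Sensordrone corresponds to (c − b)/s on the piCO+ scale. With c = 6 ppm:

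| Shared error | Equivalent piCO+ value |
|---|---|
| 10% low (s = 0.9) | 6/0.9 = 6.7 ppm |
| 30% low (s = 0.7) | 6/0.7 = 8.6 ppm |
| 1 ppm low (b = −1) | 6 + 1 = 7 ppm |

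Example: take readings of 1, 2, 3, 4, 5, 6, 7, 8, 10, 12, 15 and 20 ppm, of which 5 are below 6. At 0.7x, the readings of 6, 7 and 8 become 4.2, 4.9 and 5.6, so 8 of 12 fall below 6. Both correlations remain exactly 1.

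**2. Illustration (every input assumed; the documents give no CO distribution, noise or bias).** 60% of readings follow smoking (median 10 ppm) and 40% abstinence (median 2 ppm), log-normal with log-SD 0.3 to 0.7, and device noise is 15%. Missed means a piCO+ reading of 6 ppm or more that the Sensordrone puts below 6.

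| Sensordrone | Pearson r | Concordance coefficient | Missed |
|---|---|---|---|
| No bias | 0.965–0.980 | 0.96–0.98 | 3–4% |
| 0.9x | 0.965–0.980 | 0.955–0.973 | 8–9% |
| 0.7x | 0.965–0.980 | 0.82–0.89 | 26–29% |

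The 30% error is an arbitrary stress case. At 10% the excess over no bias is about 5 percentage points, and the missed readings lie close to the cut-off (median 6.6 to 6.9 ppm).

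**3. Would the existing data support a better measure?** Both arms used both devices in the office, which gives about 20 women. The schedule implies more than 7 pairs per intervention woman: 5 in week 1, 2 in week 2 and 1 each in weeks 4 and 8 make 9, and the baseline and 3-month assessments make 11. The stated maximum over weeks 1 to 12 is 5 + 2 + (6 × 2) + (4 × 1) = 23. Simulating 7 and 23 pairs brackets this, with the further assumption that 30% of device-error variance lies between women:

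| 95% range over simulated trials | No bias | 0.9x |
|---|---|---|
| Missed, 7 pairs | 0–10% | 3–18% |
| Missed, 23 pairs | 1.5–8% | 4.5–15% |
| Mean ratio, 7 pairs | 0.96–1.04 | 0.86–0.94 |
| Mean ratio, 23 pairs | 0.96–1.04 | 0.87–0.93 |

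The missed proportions overlap and the mean ratios do not. The 95% interval for the mean ratio excludes 1 at 0.9x in over 99% of trials at 7, 9, 11 or 23 pairs. This falls to about 93% if 70% of the error variance lies between women, to 66–73% at 30% noise, and to 88–92% with the ten intervention women alone (63–64% if, in addition, 70% of the error variance lies between women).

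**The case against.** The case for leaving the plan alone has several parts.

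- **Cotinine and calibration already check the sensor.** Partly right. The cotinine assay is described and could flag low CO in women who smoke, and calibration is meant to correct just this kind of shared error. But cotinine is a different analyte and cannot measure ppm agreement between two CO devices, and calibration has no stated tolerance. Neither lets a correlation show agreement.
- **Correlation is not blind to all device error.** Correct. Women received their own sensors, and error that varies between units does lower a pooled correlation. Under the assumptions above at 0.9x, unit-scale log-SDs of 0.1, 0.2 and 0.3 bring r down to 0.95–0.97, 0.91–0.95 and 0.85–0.90. Only the shared component goes unseen.
- **A concordance coefficient may have been meant.** None is named. In the illustration it would show a 30% error clearly and a 10% error hardly at all.
- **The cut-off and the exposed readings do not meet.** This stands. The 6 ppm value is documented only for the abstinence endpoint. The available text gives no cut-off for incentives or negative breath tests, and a figure is missing from the incentive description.
- **This is a pilot about feasibility and acceptability.** That lowers the severity. However, the Overview makes reliability and validity of the measures a stated purpose of the trial.

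A reader might infer that the Sensordrone reads low, or that the 7-day abstinence comparison favours the app arm. The documents support neither. They report no bias, the endpoint also requires self-reported abstinence, the end-of-treatment assessment lies outside remote testing, and in-person tests used both devices.

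**Conclusion.** The point holds in a limited form. Correlation, of unnamed type, is the only device-agreement statistic in the plan, and an ordinary correlation cannot register an offset or scale error common to all readings. That conclusion is algebra. So is the shift it would hide: 6 ppm on the Sensordrone equals 6.7 ppm on the piCO+ at 0.9x, or 7 ppm with a 1 ppm deficit.

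The misclassification and precision figures are illustrations and say nothing about how this sensor performed. The abstinence endpoint would be affected only if the Sensordrone supplied the verifying reading. A falsely low value would then matter only for women who also report abstinence. This is a modest weakness in one of three listed outcomes, worth correcting because the correction is cheap.

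**What to change.** Add a short device-agreement analysis, using the paired office readings already collected:

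1. **Main validity measure.** Mean Sensordrone minus piCO+ difference, with 95% limits of agreement that allow for repeated readings and confidence intervals clustered by woman. If the error grows with the reading, use the mean ratio instead, with a stated rule for 0 ppm readings, for which a ratio or logarithm is undefined.
2. **Supporting measure.** Agreement of Sensordrone below 6 ppm with piCO+ below 6 ppm (sensitivity and specificity), with a note that about 20 women cannot reliably separate a 10% scale error from none.
3. **Correlation.** Keep it as description only.

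The cost is some plan wording and a little more analysis, with no new visits or tests. The drawback is wide intervals for the cut-off agreement, which is why it should support the mean difference or ratio and not replace it.
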